Study objective(s)	
The primary objective of this study is to:
 
 • Test the activity/response rate per RECIST 1.1 criteria of anetumab ravtansine in patients with advanced pancreatic cancer who stain for mesothelin expression 
The secondary objectives of this study are to:
 
 • Time to Progression (TTP) defined as time from study treatment to RECIST progression, or death (others going off study will be censored) • Toxicity in pancreatic cancer patients (at 6.5 mg/kg dose)
Test drug(s)	Anetumab ravtansine
Name of active ingredient	Anetumab ravtansine / BAY 94-9343
Dose(s)	6.5 mg/kg every 3 weeks (Q3W)
Route of administration	Intravenous (IV) infusion over 1 h
Duration of treatment	
Patients will continue on treatment until one of the following occurs:
 
 • Progressive disease (PD) as defined by Response Evaluation Criteria in Solid Tumors (RECIST) v1.1 as assessed by Investigator. However, all scans will also be read independently by radiologists in Precision Metrics (previously known as Tumor Imaging Metrics Core [TIMC]) or an equivalent system and archived therein. • Clinical progression as assessed by investigator. • Death • Any other criterion for withdrawal from study treatment.
Reference drug(s)	Not applicable
Indication	Pre-treated advanced pancreatic cancer, Mesothelin positive by IHC
Diagnosis and main criteria for inclusion /exclusion	
Patients with advanced metastatic pancreatic cancer who have measurable disease; must have at least one and not more than two prior chemotherapy regimens for advanced disease (neoadjuvant or adjuvant chemotherapy would not be counted as a line of therapy). If prior radiation, measurable lesion outside radiation portal. ECOG PS 0-1; Mesothelin positive (defined as 30% of cells with staining 2+ or 3+ on IHC for mesothelin). Must have normal organ function with LFTs <2.5 x ULN, no history of keratitis or corneal disease. Excluded from study if have uncontrolled medical illness or infections, peripheral neuropathy interfering with function, history of corneal disease or keratitis

Study design	A nonrandomized, open-label, single arm, 2-3 center, Phase II study.

Clinical Study Protocol

19-September-2018

BAY 94-9343 (Anetumab in Pancreatic Cancer)
Version 4.0

Page: 4 of 77

	
Patients will be treated and undergo imaging scan every 6 weeks.
 
RECIST 1.1 criteria to be used for response
 
Descriptive statistics of RR (response rate) + 95% CI
 
Time to Progression calculated by K-M method
 
All patients treated with at least one dose of Anetumab to be included
 
A maximum of 30 patients will be enrolled in a minimax, Simon 2-stage design with a single early stopping rule for lack of efficacy. The target population is those patients with pancreatic cancer who have failed an earlier treatment. All patients will be treated with an anti-mesothelin immuno-conjugate, in this single arm, non-randomized trial. The endpoint is any response using the RECIST 1.1 criteria.
 
The minimax, Simon 2-stage design testing 5% null hypothesis versus a 21% alternative requires a maximum of 30 patients. If there are no patients exhibiting any response among the first 20, which indicates a response rate less than 5%, then the trial will terminate early. If there is at least one response among the first 20 (indicating response rate of at least 5%), then the trial will accrue an additional 10 patients for a maximum of 30. Four or more responses out of 30 will reject the null hypothesis in favor of the 21% response alternative. These criteria have significance level (alpha) 0.1 and power 90%. The probability of stopping early is 36% if the response rate is 5% or lower. The expected sample size is 26.4.

Methodology	
Primary efficacy will be assessed based on radiological tumor evaluation by contrast-enhanced computed tomography (CT) or contrast-enhanced magnetic resonance imaging (MRI) of chest/abdomen/pelvis. During treatment as well as active follow-up, tumor imaging will be performed with the same modality to the extent possible, every 6 weeks during the first 6 months after the start of study treatment, every 9 weeks until the end of year 2, and every 12 weeks thereafter until RECIST confirmed radiological disease progression or end of study.
 
Safety evaluations will be done at full screening, at each clinic visit during the treatment period, and at the safety follow-up visit. The National Cancer Institute's Common Terminology Criteria for Adverse Events (NCI-CTCAE) version 4.03 will be used to grade severity of adverse events (AEs).

Type of control	Not applicable
Data Monitoring Committee	Yes
Number of patients	A maximum of 30 patients will be enrolled
Primary variable	Response rate as measured per RECIST 1.1 criteria
Plan for statistical analysis	
The minimax, Simon 2-stage design testing 5% null hypothesis versus a 21% alternative requires a maximum of 30 patients. If there are no patients exhibiting any response among the first 20, which indicates a response rate less than 5%, then the trial will terminate early. If there is at least one response among the first 20 (indicating response rate of at least 5%), then the trial will accrue an additional 10 patients for a maximum of

Clinical Study Protocol

19-September-2018	BAY 94-9343 (Anetumab in Pancreatic Cancer) Version 4.0	Page: 5 of 77
-------------------	------------------------------------------------------------	---------------

30. Four or more responses out of 30 will reject the null hypothesis in favor of the 21% response alternative. These criteria have significance level (alpha) 0.1 and power 90%. The probability of stopping early is 36% if the response rate is 5% or lower. The expected sample size is 26.4.

Contents

1.	Title page.....	1
2.	Synopsis	3
3.	Introduction.....	14
3.1	Background.....	14
3.2	Rationale of the study.....	15
4.	Study objectives	15
5.	Study design.....	15
5.1	Design overview	15
5.2	Primary variable	16
6.	Study population	16
6.1	Inclusion criteria.....	16
6.1.1	Eligibility criteria for prescreening	16
6.1.2	Eligibility criteria for full study	17
6.2	Exclusion criteria.....	18
6.3	Withdrawal of patients from study.....	20
6.3.1	Screening failure	20
6.3.2	Withdrawal criteria.....	21
6.3.3	Lost to follow-up patients	23
6.3.4	General withdrawal procedures.....	23
6.3.5	Replacement.....	23
6.4	Patient identification.....	23
7.	Treatment(s).....	23
7.1	Treatments to be administered.....	23
7.2	Identity of study treatment.....	23
7.2.1	Test drug - anetumab ravtansine	23
7.3	Dosage and administration	25
7.3.1	Administration of anetumab ravtansine	25
7.3.2	Dose modification	25
7.4	Drug logistics and accountability	35
7.5	Treatment compliance	36
8.	Non-study therapy	36
8.1	Prior and concomitant therapy.....	36
8.2	Post-study therapy	39
9.	Procedures and variables.....	40

Clinical Study Protocol

19-September-2018

BAY 94-9343 (Anetumab in Pancreatic Cancer)

Version 4.0

Page: 7 of 77

9.1	Tabular schedule of evaluations	40
9.2	Visit description.....	42
9.2.1	Prescreening	42
9.2.2	Full screening period.....	43
9.2.3	Treatment period	44
9.2.4	Efficacy assessments	48
9.2.5	Follow-up periods	48

Table2 -5	Doseadjustmentsinresponsetonon -hematologictoxicities	30
Table2 -6	Bayerclassificationandmanagementofcornealepitheliopathies	32
Table2 -7	Bayerclassificationofvisualacuitychanges	35
Table2 -8	Prohibitedpriorandconcomitanttherapies	37
Table2 -9	Permittedconcomitanttherapies	39

Table of figures

Clinical Study Protocol

19-September-2018 BAY 94-9343 (Anetumab in Pancreatic Cancer) Page: 9 of 77
Version 4.0

Figure2 -1 Withdrawalcriteria22

List of abbreviations

5-HT3	5-hydroxytryptamine (serotonin)
ADC	Antibody-drug conjugate
AE	Adverse event
AG	Joint stock company, Aktiengesellschaft
ALP	Alkaline phosphatase
ALT	Alanine aminotransferase
ANC	Absolute neutrophil count
aPTT	Activated partial thromboplastin time
ASCO	American Society of Clinical Oncology
AST	Aspartate aminotransferase
BCVA	Best corrected visual acuity
β -HCG	β subunit of human chorionic gonadotropin
BIO	Biomarker set
BM	Biomarker
BP	Blood pressure
BSA	Body surface area
BUN	Blood urea nitrogen
$^{\circ}$ C	Celsius degree(s)
C	Cycle
CBC	Complete blood count
C_{max}	Maximum drug concentration
CNS	Central nervous system
COA	Clinical Outcomes Assessment
CR	Complete response
CRF	Case report form
CSF	Colony stimulating factor
CSR	Clinical Study Report
CT	Computed tomography
CTCAE	Common Terminology Criteria for Adverse Events
CYP2D6	Cytochrome P450, family 2, subfamily D, polypeptide 6
CYP3A4	Cytochrome P450, family 3, subfamily A, polypeptide 4
D	Day
dL	Deciliter
DM4	Derivatives of maytansine 4
DM4-Me	Methyl-DM4
DSMC	Data and Safety Monitoring Committee
DNA	Deoxyribonucleic acid
DOR	Duration of response
ECG	Electrocardiogram
EchoCG	Echocardiogram
ECOG	Eastern Cooperative Oncology Group
ECOG PS	Eastern Cooperative Oncology Group Performance Status
EDC	Electronic data capture
eGFR	Estimated glomerular filtration rate

ENR Enrolled set

Clinical Study Protocol

19-September-2018

BAY 94-9343 (Anetumab in Pancreatic Cancer)

Version 4.0

Page: 11 of 77

ETDRS	Early Treatment Diabetic Retinopathy Study
EU	European Union
°F	Fahrenheit degree(s)
FDA	Food and Drug Administration
FFPE	Formalin-fixed, paraffin-embedded
g	Gram(s)
GCP	Good Clinical Practice
G-CSF	Granulocyte-colony stimulating factor
GFR	Glomerular filtration rate
GGT	Gamma-glutamyl transferase
GMP	Good Manufacturing Practice
GPV	Global Pharmacovigilance
h	Hour(s)
H0	Null hypothesis
HA	Alternative hypothesis
Hb	Hemoglobin
HIC	Human Investigation Committee
HIV	Human immunodeficiency virus
HR	Heart rate
IB	Investigator's brochure
ICF	Informed consent form
ICH	International Conference on Harmonization
IDS	Investigational Drug Service
IEC	Independent Ethics Committee
IgG1	Immunoglobulin G subclass 1
IHC	Immunohistochemistry
ILD	Interstitial lung disease
IM	Immunogenicity
IMP	Investigational medicinal product
INR	International normalized ratio
IOP	Intraocular pressure
IRB	Institutional Review Board
ITT	Intent-to-treat (set)
IUD	Intrauterine device
IUS	Intrauterine hormone-releasing system
IV	Intravenous
kg	Kilogram(s)
LDH	Lactic dehydrogenase
LLN	Lower limit of normal
LPLV	Last patient last visit
LVEF	Left ventricular ejection fraction
m ²	Square meter(s)
MCU	Multi-Center Unit
MD	Doctor of Medicine

Clinical Study Protocol

19-September-2018

BAY 94-9343 (Anetumab in Pancreatic Cancer)

Version 4.0

Page: 12 of 77

MDRD	Modification of Diet in Renal Disease
MedDRA	Medical Dictionary for Regulatory Activities
mg	Milligram(s)
Min	Minute(s)
miRNA	Micro ribonucleic acid
mL	Milliliter(s)
mm ³	Cubic millimeter(s)
mmHg	Millimeter of mercury
MoA	Mechanism of action
mRECIST	Modified Response Evaluation Criteria in Solid Tumors
MRI	Magnetic resonance imaging
MTD	Maximum tolerated dose
MUGA	Multiple gated acquisition
N	Number of patients
n	Number of non-missing values
N HCl	Normal hydrochloric acid
NC	No change
NCCN	National Comprehensive Cancer Network
NCI-CTCAE	National Cancer Institute's Common Terminology Criteria for Adverse Events
NE	Not evaluated
NGS	Next generation sequencing
NYHA	New York Heart Association
ORR	Objective response rate
OS	Overall survival
PD	Progressive disease
PET	Positron emission tomography
PFS	Progression-free survival
PFT	Pulmonary function test
P-gp	Permeability glycoprotein
PhD	Doctor of Philosophy
PI	Principal Investigator
PK(s)	Pharmacokinetic(s)
PR	Partial response
PT	Prothrombin time
PTT	Partial thromboplastin time
Q3W	Every 3 weeks
QA	Quality assurance
QW	Once weekly
RECIST	Response Evaluation Criteria in Solid Tumors
RNA	Ribonucleic acid
RPIID	Recommended Phase II dose
RR	Respiratory rate
RT	Radiotherapy
SAE	Serious adverse event

Clinical Study Protocol

19-September-2018

BAY 94-9343 (Anetumab in Pancreatic Cancer)

Version 4.0

Page: 13 of 77

SAF	Safety set
SAP	Statistical Analysis Plan
SAS	Statistical Analysis Software
SD	Stable disease
SoC	Standard of care
SPDB	N-succinimidyl 4-(2-pyridyldithio)butyrate (reducible disulfide linker)
SPK	Superficial punctate keratitis
SQR RT	Square root ($\sqrt{\quad}$)
SUSAR	Suspected, unexpected, serious adverse reaction
T1	Tumor invades lamina propria
Ta	Non-invasive tumor
TEAE	Treatment-emergent adverse event
Temp	Body temperature
Tis	Carcinoma in situ
TMF	Trial master file
TTP	Time to progression
ULN	Upper limit of normal
US(A)	United States of America
USP	United States Pharmacopeia
WBC	White blood cell count
WOCBP	Women of childbearing potential
YCC	Yale Cancer Center
YCCI	Yale Center for Clinical Investigation

3. Introduction

3.1 Background

Mesothelin is a membrane associated differentiation antigen present on normal mesothelial cells and overexpressed in a vast majority of ductal pancreatic adenocarcinomas, mesotheliomas, and adenocarcinomas of the ovary. The biological function of mesothelin remains unknown and mesothelin-deficient mice have no obvious phenotype of defect. Mesothelin is an internalizing antigen and shows a restricted expression profile in normal tissue making it an excellent target for antibody directed cytotoxic drug delivery.

BAY 94-9343, anetumab ravnansine, is an antibody-drug conjugate consisting of a fully human IgG1 antibody (MF-T, BAY 86-1903) directed at the mesothelin antigen and conjugated to a synthetic cytotoxic anticancer agent, maytansine derivative (DM4, BAY 1006640) as toxophore through a reducible disulfide linker (SPDB). Preclinical efforts have shown specific effects on mesothelin positive cell lines and in xenograft models including activity in pancreatic BxPC3 xenograft model. Toxicology studies showed a number of important signals but specifically skin toxicity.

Human phase 1 and PK studies were performed showing terminal phase half-life values of the ADC and Total Antibody were approximately 5.5 to 6 days. Plasma DM4 and DM4-Me concentrations declined with a half-life of approximately 3 days and 5.5 days at the MTD. DM4-Me pharmacokinetics exhibited moderate to high variability and exposure increased in a substantially more than dose proportional manner in the dose range studied.

The safety results from the dose escalation part of the first-in-human study 15051 in 45 patients with advanced cancer (BAY 94-9343 dose range, 0.15-7.5 mg/kg q3w) were as follows: 1) The non-tolerable dose of BAY 94-9343 was 7.5 mg/kg q3w; the non-tolerable toxicities at 7.5 mg/kg q3w were corneal toxicity (blurry vision and keratitis due to corneal epitheliopathy), peripheral neuropathy and increase in serum amylase and lipase; 2) The maximum tolerated dose was 6.5 mg/kg q3w; the only dose-limiting toxicity observed at this dose level was the asymptomatic Grade 3 increase in serum AST/ALT; 3) The most common treatment-emergent adverse events at least possibly related to BAY 94-9343 were fatigue, nausea, vomiting, anorexia, peripheral neuropathy, myalgia, weakness and diarrhea. The most common treatment-emergent lab abnormalities were lymphopenia, hypoalbuminemia, hyponatremia, hyperglycemia and hypokalemia; 4) at doses below the non-tolerated dose, the TEAEs were mostly mild and not clinically significant except for cardiac chest pain, hypertension, grade 3 increase in ALT and AST, and decrease in platelets and sodium.

The safety results from the MTD Expansion 6.5 mg/kg q3w cohort, which evaluated the MTD for BAY 94-9343 determined in the dose escalation cohorts were as follows: 1) BAY 94-9343 at 6.5 mg/kg given IV once every 3 weeks was considered tolerable in the two cohorts of subjects with ovarian cancer (n=20) and pleural or peritoneal mesothelioma (n=12); 2) Overall, 16 of 32 (50%) subjects treated at 6.5 mg/kg q3w have required dose reduction to 5.5 mg/kg q3w and 4 (25%) of these subjects required another dose reduction to 4.5 mg/kg; 3) the safety finding of particular relevance was the high incidence of corneal toxicity (blurred vision and keratitis with vision impairment due to corneal epithelial microcysts or deposits in 12 of 32 subjects) causally attributed to BAY 94-9343; 4) although being fully reversible in the vast majority of cases, the corneal toxicity invariably necessitated lengthy treatment interruption and dose reduction; 5) otherwise the safety profile of BAY 94-9343 in the MTD

Expansion 6.5 mg/kg q3w cohort was very similar to that observed in dose escalation cohorts up to and including the Cohort 9 (6.5 mg/kg q3w), with mostly mild TEAEs and remarkably low incidence of drug-related SAEs. One patient in a Japanese cohort with pancreatic cancer developed drug-induced liver injury.

We will therefore pursue the 6.5 mg/kg dose, as having an acceptable incidence of corneal toxicity and keratitis and as the phase II dose in use for current studies.

3.2 Rationale of the study

The need for new treatments for pancreatic cancer is great. At the MTD of 6.5 mg/kg Q3W, anetumab ravtansine has demonstrated a tolerable safety profile and efficacy in pancreatic cancer. If this study shows promise, with at least 21% of treated patients showing RECIST response, or prolonged delay in progression compared with historical controls, this would suggest the potential to impart large clinical benefit and warrant larger controlled trials.

4. Study objectives

The primary objective of this study is to:

- Test the activity/response rate per RECIST 1.1 criteria of anetumab ravtansine in patients with advanced pancreatic cancer who stain for mesothelin expression

The secondary objectives of this study are to:

- Time to Progression (TTP) defined as time from study treatment to RECIST 1.1 progression, or death (others going off study will be censored)
- Toxicity in pancreatic cancer patients (at 6.5 mg/kg dose)

5. Study design

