5.1 Design overview

This is a non-randomized, open-label, multicenter, Phase II study to evaluate the efficacy and safety of intravenous anetumab ravtansine (BAY 94-9343), an anti-mesothelin antibody drug conjugate, in pretreated mesothelin-expressing advanced pancreatic cancer.

At the time of the start of study treatment, the patients will have pretreated advanced pancreatic cancer that also overexpresses mesothelin as determined by immunohistochemistry (IHC). Mesothelin testing will be performed centrally.

A maximum of 30 patients will be enrolled in a minimax, Simon 2-stage design with a single early stopping rule for lack of efficacy. The target population is those patients with pancreatic cancer who have failed an earlier treatment. All patients will be treated with an anti-mesothelin immuno-conjugate, in this single arm, non-randomized trial and all patients treated with at least one dose of Anetumab will be included. The endpoint is any response using the RECIST 1.1 criteria.

The minimax, Simon 2-stage design testing 5% null hypothesis versus a 21% alternative requires a maximum of 30 patients. If there are no patients exhibiting any response among the first 20, which indicates a response rate less than 5%, then the trial will terminate early. If there is at least one response among the first 20 (indicating response rate of at least 5%) then the trial will accrue an additional 10 patients for a maximum of 30. Four or more responses out of 30 will reject the null hypothesis in favor of the 21% response alternative. These

criteria have significance level (alpha) 0.1 and power 90%. The probability of stopping early is 36% if the response rate is 5% or lower. The expected sample size is 26.4.

The start of the treatment period is defined by first administration of study drug (anetumab ravtansine). Patients will receive anetumab ravtansine IV infusion at a dose of 6.5 mg/kg (recommended Phase II dose [RPIID]) on Day 1 of a 21-day cycle. Treatment will be continued until death or occurrence of PD as defined by Response Evaluation Criteria in Solid Tumors (RECIST) v1.1 and assessed by blinded radiology review, or clinical progression, or until another criterion for withdrawal from the study is met.

Patients who discontinue study treatment for any reason other than confirmed radiological PD will be followed for progression during active follow-up (which includes the safety follow-up period) until confirmed PD for this patient is observed.

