6.3.5 Replacement

No replacement of patients will be allowed during this study.

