10.1 General considerations

Statistical analysis will be performed using SAS version 9.2 or later; the version used will be specified in the SAP.

In general, continuous variables will be summarized using number of non-missing values (n), number of missing values, means, standard deviations, medians, maximum, minimum, and interquartile range.

Ordinal variables will be summarized using n, number of missing values, medians, maximum, minimum, and interquartile range.

Categorical variables will be summarized using n, number of missing values, and percentages.

Time-to-event variables will be summarized using Kaplan-Meier estimates.

Further details on the statistical analyses will be provided in the SAP.

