10.2.2.1 Primary efficacy analysis

The primary efficacy analysis tests the following hypotheses:

H0: In patients with advanced or metastatic pancreatic cancer overexpressing mesothelin and pretreated with prior chemotherapy, a response per RECIST under treatment with anetumab ravtansine at 6.5 mg/kg Q3W would not be seen.

versus

HA: In patients with advanced or metastatic pancreatic cancer overexpressing mesothelin and pretreated with prior chemotherapy, a response per RECIST under treatment with anetumab ravtansine at 6.5 mg/kg Q3W would be seen.

The minimax, Simon 2-stage design testing 5% null hypothesis versus a 21% alternative requires a maximum of 30 patients. If there are no patients exhibiting any response among the first 20 then the trial will terminate early. If there is at least one response among the first 20 then the trial will accrue an additional 10 patients for a maximum of 30. Four or more responses out of 30 will reject the null hypothesis in favor of the 21% response alternative. These criteria have significance level (alpha) 0.1 and power 90%. The probability of stopping early is 36% if the response rate is 5% or lower. The expected sample size is 26.4.

Sensitivity analyses will be performed, including analyses to assess the impact of missing data and the possibility of survivorship and selection biases. Further details will be described in the SAP.

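### Does the 21% response in the Section 3.2 rationale conflict with the rule of 4 responses in 30?

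*Combined protocol and SAP*

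**What the plan says.** Section 3.2 (Rationale) says the study would show promise "with at least 21% of treated patients showing RECIST response, or prolonged delay in progression compared with historical controls", and that this would justify larger controlled trials.

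Section 10.2.2.1 states the decision rule: "Four or more responses out of 30 will reject the null hypothesis in favor of the 21% response alternative". Both synopsis entries (study design; plan for statistical analysis) and Section 5.1 give the same rule: 5% null, 21% alternative, stop if none of the first 20 respond, otherwise go on to 30, with alpha 0.1 and power 90%. Section 10.2.2.1 adds: "The probability of stopping early is 36% if the response rate is 5% or lower".

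On the analysis set, Section 5.1 says "all patients treated with at least one dose of Anetumab will be included", and Section 6.3.5 says "No replacement of patients will be allowed during this study".

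On reporting, the synopsis plans "Descriptive statistics of RR (response rate) + 95% CI" and "Time to Progression calculated by K-M method". Section 10.1 says the same in general terms: "Time-to-event variables will be summarized using Kaplan-Meier estimates".

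**The concern.** Four things look wrong on a first reading.

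- **Two bars for response.** In the design, 21% is the true rate at which power is computed. Section 3.2 uses the same figure as a proportion seen in treated patients. That needs more responses than the rule does, so a trial could reject the null and still fall short of Section 3.2.
- **A second route with no benchmark.** Section 3.2 offers delayed progression against historical controls as an alternative. The document names no historical source, value or criterion. A trial that failed on response might then be called promising against a comparator chosen after the data are seen.
- **Early stopping.** The 36% is stated for any response rate up to 5%, but it is exact only at 5%.
- **Interval and test.** A two-sided 95% interval can include 5% when the rule rejects 5%.

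At stake is how a result of 4 to 6 responses, or a favourable time to progression with few responses, would be described when a larger trial is considered.

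**Working it through.** **Inputs** (Sections 5.1 and 10.2.2.1): n1 = 20, stop at 0 responses; n2 = 10, N = 30; reject at 4 or more; p0 = 0.05, p1 = 0.21. The 21% figure read as an observed proportion comes from Section 3.2.

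**Step 1. Reproduce the plan's figures.**

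- P(stop early) = (1 − p)^20. At p = 0.05: 0.95^20 = 0.3585 (stated 36%).
- Expected size = 20 + 10 × (1 − 0.3585) = 26.4 (stated 26.4).
- P(at least r responses) = Σ over x = 1 to 20 of P(X1 = x) × P(X2 ≥ r − x), with X1 ~ Bin(20, p) and X2 ~ Bin(10, p).
- With r = 4: 0.0604 at p = 0.05, inside the 0.10 limit, and 0.9003 at p = 0.21 (stated 90%).

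A search over smaller maximum sizes finds none that meets both limits. At N = 30, the split of 20 + 10 with rejection at 4 has the smallest expected size under the null, so the design is the minimax one it claims to be.

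**Step 2. Turn Section 3.2 into a count.** 0.21 × 30 = 6.3, so 7 responses are needed: 6/30 = 20.0% falls short and 7/30 = 23.3% meets it. The rule needs 4/30 = 13.3%.

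**Step 3. Size of the gap** (same formula, r = 4 and r = 7).

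| True rate | P(≥ 4) | P(≥ 7) | P(4 to 6) |
|---|---|---|---|
| 5% | 0.0604 | 0.0006 | 0.0598 |
| 15% | 0.6764 | 0.1526 | 0.5238 |
| 21% | 0.9003 | 0.4470 | 0.4533 |

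If 7/30 were the operating rule, power at 21% would be 45%, and 90% would need a true rate of about 32.5%. No section adopts that rule.

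The gap does not hinge on exactly 30 treated. As an assumption, suppose 28 are treated, both losses fall in stage 2, and the cut-off stays at 4. Then 0.21 × 28 = 5.88, so 6 responses meet 21%, and at a true 21% P(4 or 5) = 0.8679 − 0.5520 = 0.3159.

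**Step 4. Early stopping below 5%.** 0.96^20 = 0.442 and 0.97^20 = 0.544. So 36% is the minimum over the stated range, and the wording understates how often an inactive drug stops early. The rule itself is the same.

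**Step 5. Interval against rule** (exact Clopper–Pearson limits, ignoring the two-stage stopping).

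- 4/30: 95% limits 3.8% to 30.7%, which include 5%.
- 5/30: 95% limits 5.6% to 34.7%, which exclude 5%.
- 4/30: 80% limits 5.9% to 24.9%. This interval matches a one-sided 0.10 test and excludes 5%.

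Interval and decision part company only at exactly 4 responses, which has probability 0.1153 at a true 21%. The reason is a one-sided 0.10 test set beside a two-sided 95% interval. The synopsis presents the interval as a descriptive statistic, and no section makes it a criterion.

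**Step 6. Set the texts side by side.** Section 10.2.2.1 says when the 5% null is rejected. Section 3.2 says what would suggest a large clinical benefit and justify larger trials. These are different questions. Section 3.2 gives sufficient conditions and is silent on 4 to 6 responses, so such a result contradicts neither text.

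**The case for a change.** The best case for a change is that Section 3.2 is the only text tying results to the next development step, so readers will turn to it when 4 to 6 responses are seen, and that outcome is common at the design's own target rate. The progression route, joined by an 'or' and lacking a benchmark, also leaves room for a favourable reading after the fact. A clarifying sentence would cost almost nothing.

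The facts behind this stand: 21% is used in two senses, and the document gives no historical benchmark. Sections 10.1 and 10.2.2.1 leave further analysis detail to a SAP, so the absence here is weak evidence that none was intended.

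The step to a required change does not stand. Declaring that 4/30 supports larger trials would lower the sponsor's stated bar from 21% to 13.3%, a result whose 95% interval starts at 3.8%. Ruling out progression would be a new restriction. Both are development decisions. A sponsor may reasonably ask more before a larger trial than rejection of 5%. A neutral note that 21% is the design alternative would be harmless, but it would alter no analysis and no result.

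Sections 9.4 and 10.2.2 describe the primary variable in progression terms. That is a separate matter, and rewording Section 3.2 would not settle it.

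**Conclusion.** No change is needed. The 4/30 rule is correct, is stated consistently in both synopsis entries and in Sections 5.1 and 10.2.2.1, and has attained alpha 0.060 and power 0.900. Section 3.2 alters neither. The 45% chance of 4 to 6 responses at a true 21% is the chance of a result on which the rationale is silent; it is not a loss of power. The early-stopping phrase is a loose statement of a figure that is right at 5%. The mismatch between interval and test is confined to exactly 4/30 and is ordinary for a one-sided 0.10 design reported with a 95% interval.

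This rests on reading Section 3.2 as rationale and Section 10.2.2.1 as the governing rule, and on all 30 patients being treated if the trial passes stage 1. If the sponsor meant Section 3.2 as a formal go/no-go criterion, its count and its progression benchmark would need pre-specifying, but nothing in the document says so.
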